## 14.0 Risks to Subjects

### 14.1 Loss of Confidentiality.

All studies carry some risk for the potential loss of confidentiality. Every effort will be made to protect your information. Protection of patient confidentiality is essential in human clinical trials. A HIPAA compliant de-identification process will be utilized which includes a unique computer-generated study ID for each enrolled subject. Patient data maintained outside of the study site and within the WebDCU will be stored in coded format with the key maintained with the local site PI. Furthermore, study binders will be maintained in locked physical facilities and only accessible to authorized study team members to protect patient privacy.

### 14.2 Interviews & Questionnaires.

Some of the questions the researchers ask may be upsetting or may make patients feel uncomfortable answering. If the patient does not want to answer a question, they may skip it and go to the next question.

### 14.3 Quantitative Sensory Testing.

The procedure proposed in this study are widely used to research and clinical practice and have been shown to be safe. For thermal pain procedures, the stimulator will be set with a limit of 50°C which is well below the threshold for causing any damage to the subject's skin or nerve endings. However, it is not unusual to experience some tenderness, redness or inflammation in the heated skin area after completion of the thermal pain procedures. These symptoms subside within a few hours with no intervention. For mechanical stimulation procedures, the range of von Frey Hair weights (digital and analog) to be used for stimulation will be incapable of breaking the skin or doing any tissue damage.

### 14.4 Endoscopic ultrasound (EUS).

Risks of EUS include bleeding, heart or lung problems, infection, or inflammation at the intravenous (IV) site, perforation and adverse reaction to medication.

### 14.5 Randomization.

Subjects will be assigned to receive the EUS procedure only or the EUS + ERCP with endotherapy procedure by chance. One treatment group may prove to be less beneficial or have more risks than the other group.

### 14.6 Blinding.

To keep free from bias, the protocol has been carefully developed to minimize risk of unmasking subjects and investigators responsible for evaluating subjects during follow-up. If a subject develops a medical problem where it is important for treating providers to know whether or not an ERCP was performed, there will be a mechanism in place for urgent unmasking of treating provider through the Statistical and Data Coordination Center (SDCC).

### 14.7 Sham.

Subjects in the sham group will not receive ERCP with endotherapy. While these subjects will not be exposed to the risks specific to ERCP, including post-ERCP pancreatitis, subjects will not receive the potential benefit which may occur from the ERCP procedure.

### 14.8 ERCP.

If randomized to ERCP plus endotherapy, the procedure will be performed immediately after EUS and under the same anesthetic. Subjects undergoing ERCP will be at risk for the ERCP specific complications which includes post-ERCP pancreatitis (5-10%).

**14.9 Indomethacin.** Indomethacin is used in clinical practice to prevent post-ERCP pancreatitis, but is not FDA approved for this indication. Long or medium-term use of non-steroidal anti-inflammatory drugs (NSAIDs), such as indomethacin, is associated with several adverse events including peptic ulcer disease, kidney failure, heart attack, stroke, and worsening of congestive heart failure or high blood pressure. The risk of these adverse is related to the duration of use. A single dose of indomethacin is extremely unlikely to cause the biochemical, hormonal, and physiological changes necessary to induce such events.

**14.10 Endotherapy.** The risks of endotherapy involve bleeding around the site, infection, or obstruction caused by the fragments of material created by the endotherapy that may require more endotherapy to remove.

**14.11 Stent Placement.** There is a chance that the stent placement could be placed within or migrate into the duct and cause pancreatitis, infection, or perforation. Migrated stents can be difficult to retrieve and may require an operation.

## 15.0 Potential Benefits to Subjects or Others

**15.1 Potential benefits to the study subjects.** If ERCP with pancreatic endotherapy improves pain, quality of life, or other outcome measures of interest, then subjects randomized to the treatment arm (EUS + ERCP with pancreatic endotherapy) will have benefited from this intervention. If this hypothesis is refuted, then subjects randomized to EUS alone (EUS + sham) will have avoided a potentially harmful intervention (ERCP with pancreatic endotherapy).

**15.2 Potential benefits to science and society.** The results of this study are expected to provide preliminary data required to plan a definitive clinical trial evaluating pancreatic endotherapy. Such a trial would be expected to have a direct and immediate impact on patient care irrespective of the final outcome. Currently, the decision to perform ERCP with pancreatic endotherapy is physician-specific and a topic of repeated controversy among experts. If the study proves that ERCP with pancreatic endotherapy improves pain (or other relevant outcomes), then this practice will be adopted more widely across the world. However, if the study refutes the hypothesis that ERCP with pancreatic endotherapy reduces pain, then the practice of performing ERCP with pancreatic endotherapy for painful chronic pancreatitis would be expected to diminish significantly.

## 16.0 Sharing of Results with Subjects

The results of the initial randomization procedures will not be shared with the participants until completion of the study. However, if the subject's doctor recommends additional procedures during the course of the study, the results of these procedures will be shared with the participant.

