### 10.1.3 Follow-up visits, day 0 -90

The subject will be contacted by telephone at day 7 and 30, and complete the Ecological Momentary Assessment during this 30-day period. After the 30 day follow up phone call is complete, the participant will be compensated \$50 for their time. Thereafter, follow-up will

be on an as-needed basis until the subject returns on day 90 for the first formal follow-up assessment (details in *table 3*). The discussion regarding next steps in treatment will occur between the subject, a blinded gastroenterologist, and a blinded hepatobiliary surgeon. A multidisciplinary discussion between patient, endoscopist, and surgeon complies with society guidelines. In the case of medical management, this will be directed by the blinded physicians. In the event of an emergency room or inpatient hospitalization due to abdominal pain or other symptoms potentially attributable to chronic pancreatitis, a blinded physician will determine whether repeat endoscopic or surgical intervention is warranted before the 90-day outcome assessment. In the event that the patient is referred for repeat endoscopic or surgical intervention before reaching the 90-day outcome assessment, the Ecological Momentary Assessment tool will be reactivated in order to capture pain data for up to 14 days leading up to and including the day of intervention, as feasible. Rather than assuming no change from baseline in pain scores for those that have a re intervention prior to day 90, we will capture the pain score prior to re intervention and use these data to calculate the change score for the primary analysis.

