The day 90 follow-up assessment will include completion of selected instruments and a discussion with blinded physician investigators about their clinical course. It is not realistic to assign a threshold pain score above which further intervention should be offered, so it is expected that the blinded physicians and patient will decide whether an intervention is required to treat pain; this highlights the importance of the study's sham design. Potential scenarios are detailed in *figure 2*. Although not incorporated into this study's pilot primary outcome, it is expected that a decision to proceed with an intervention to treat pain would be considered a "failure" of pancreatic endotherapy in a definitive clinical trial. Each of the groups in figure 2 are explained in further detail below. The design of the hierarchical diagram is deliberate and intends to illustrate that management options for groups 3 and 4 are the same. In addition, follow-up is in part dependent on the original treatment allocation. So, after all blinded assessments have been completed and a decision regarding intervention determined, an unblinded investigator will need to advise the subject regarding next steps. Participants will be compensated \$75 after completing the 90-day follow up visit. If participants complete all visits, they will be compensated a total of \$200.

**1. Sham group, no intervention advised.** In this scenario, the subject is doing well enough that no intervention is advised. Since no procedures have been performed until this point, continued medical management is reasonable. The subject would be followed through day 360 for relevant changes in clinical course and to assess secondary endpoints.

[figure not shown]
**2. Endotherapy group, no intervention advised.** In this scenario, the subject is doing well enough that no intervention is advised. Since pancreatic endotherapy had been performed during the randomization procedure, the subject would be advised to undergo repeat pancreatic endotherapy to remove pancreatic duct stents. In some cases, the treating endoscopist may recommend replacing or upsizing stents in an effort to minimize stricture recurrence. This will be determined by the unblinded treating physician per standard of care. Follow-up procedures would be open-label, although it is possible that the subject remain blinded to their original treatment allocation.

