## 13.0 Withdrawal of Subjects

- The participant has the right to voluntarily withdraw consent from the study at any time for any reason without prejudice to his/her future medical care by the physician or at the institution. For the occasional participant who withdraws consent, the date and reason for consent withdrawal should be documented. Participant data will be included in the analysis up to the date of the consent withdrawal.
- A distinction should be made between participants who fail to complete all forms on schedule, who miss some telephone visits, and the withdrawal of consent. Missed or rescheduled visits will be documented, but the participant will continue to be followed in the future according to protocol requirements, and all follow-up data will be included in the analysis.
- If the participant withdraws consent for the protocol intervention and/or study related procedures, document whether the participant is willing to allow the submission of continued follow-up information. This documentation should include whether the subject will continue to be willing to be contacted during

follow-up to complete all questionnaires, or at a minimum will be willing to be contacted to provide information on quality of life.

- Investigators and/or the sponsor may stop a subject's participation in the study at any time if they decide it is in the subject's best interest. They may also do this if the subject does not follow the investigator's instructions.

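### The protocol requires no stent check, disclosure or removal referral for a blinded endotherapy subject who leaves the trial before stent removal

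*Combined protocol and SAP*

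**What the plan says.** **Stents at day 0.** Section 3.1 expects most patients with main-duct stones or strictures to need at least one stent. Section 10.1.2 makes placement of a stent across the dominant obstruction the test of overall technical success. Section 3.1 also has stent details recorded at the randomization ERCP.

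**Planned removal.** Stent removal or exchange appears in Table 1 in the day-90 row, if a stent is present and needs it. Section 10.1.3 says that "after all blinded assessments have been completed and a decision regarding intervention determined, an unblinded investigator will need to advise the subject regarding next steps". In scenario 2 (endotherapy arm, doing well), "the subject would be advised to undergo repeat pancreatic endotherapy to remove pancreatic duct stents". Scenario 4 (endotherapy arm, doing poorly) also provides for stent removal where applicable.

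**Early exit.** Section 13 allows consent withdrawal at any time and says that "the date and reason for consent withdrawal should be documented". For a subject who withdraws only from the intervention or study procedures, it also asks for a record of willingness to be followed. It adds that "Investigators and/or the sponsor may stop a subject's participation in the study at any time", either in the subject's best interest or because instructions were not followed. Withdrawal is "without prejudice to his/her future medical care by the physician or at the institution".

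**Disclosure.** Section 16 states that "The results of the initial randomization procedures will not be shared with the participants until completion of the study". The exception applies if the subject's doctor "recommends additional procedures during the course of the study, the results of these procedures will be shared with the participant".

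**The concern.** The trial places a device that its own plan says should be reviewed for removal or exchange, and it keeps the recipient from knowing whether the device is there. That is acceptable while the subject stays in follow-up, because an unblinded investigator steps in at day 90. A subject who leaves earlier loses that step. They may recall from consent that a stent was possible, but they cannot know whether one was placed. They may therefore not seek removal or mention it to a new physician.

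The harm is the one the protocol names. Section 14.11 lists migration, pancreatitis, infection and perforation, and says that retrieving a migrated stent may need an operation. Section 2.4 lists symptomatic strictures caused by pancreatic stents as a long-term adverse event. Scenario 2 shows that feeling well is not, in this plan, a reason to leave a stent unreviewed.

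The concern is limited to full consent withdrawal and to stops by the investigator or sponsor. Subjects who only miss or reschedule visits stay in follow-up under section 13.

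**Working it through.** The plan gives no figure on this point, so there is none to reproduce. The check is to follow one subject through the text: endotherapy arm, stented at day 0, no symptoms, leaves before day 90.

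1. **Is a stent likely?** Yes, from sections 3.1 and 10.1.2.
2. **Does a planned contact before day 90 deal with it?** No. Table 1 has telephone calls at days 7 and 30 about procedure-related adverse events. After that, section 10.1.3 provides follow-up only as needed.
3. **Does leaving trigger a stent step?** No. For consent withdrawal, section 13 asks for documentation. For a stop by the investigator or sponsor, it sets no exit procedure. It does not mention stents, unmasking or referral.
4. **Does another route reach this subject?**

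| Route | Trigger | Does it require telling an asymptomatic leaver? |
|---|---|---|
| Emergency or inpatient review (10.1.3) | Pain or other symptoms | No |
| Urgent unmasking (14.6) | A medical problem for which the provider needs to know | No; it informs the provider |
| Care preserved after withdrawal (13) | The subject seeks care | No; it keeps access open but conveys no information |
| Research monitor (12.1) | General safety authority | No; there is no stent procedure |
| Section 16 exception | An additional procedure | No; it covers the new procedure's results |

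5. **What does section 16 add?** Read literally, it holds back the day-0 results and makes no exception for early exit. Study completion is not defined. It could mean the subject's day-360 visit, the end of the trial, or the subject's own exit. On none of these readings does section 13 require disclosure at exit.

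**Scale.** Section 11.2 gives 15 subjects per arm, so the ceiling is 15. No exit rate is stated. As an illustration only, let p be the assumed chance that an endotherapy subject leaves early with a stent in place. The expected number is 15 × p, and the chance of at least one is 1 − (1 − p)^15.

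| Assumed p | Expected number | Chance of at least one |
|---|---|---|
| 2% | 15 × 0.02 = 0.3 | 1 − 0.98^15 = 26% |
| 5% | 15 × 0.05 = 0.75 | 1 − 0.95^15 = 54% |
| 10% | 15 × 0.10 = 1.5 | 1 − 0.90^15 = 79% |
| 20% | 15 × 0.20 = 3.0 | 1 − 0.80^15 = 96% |

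The documents point to the lower rows: section 13 describes withdrawal as occasional, and section 5.2 excludes patients unlikely to complete follow-up.

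**The case against.** The best reply is that silence is not prohibition. Section 16 is a blinding rule and does not forbid clinical care. The day-0 endoscopist knows of the stent, its details are on record, and scenario 2 leaves stent decisions to an unblinded treating physician under standard of care. These patients were referred to two expert centers, and section 13 keeps their access to care. A stop made in the subject's best interest implies that a clinician has thought about that subject. Exit advice may also sit in the consent material, which was removed from the review copy.

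All of this lowers the probability of harm, and it stands to that extent. It does not supply a required step. Good practice by one informed endoscopist is likely, but it is not assured, and a literal reading of section 16 gives that endoscopist no support for speaking.

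Three stronger readings are tempting and should be resisted.

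- A reader might infer from "In the case of medical management, this will be directed by the blinded physicians" that whoever handles an exit before day 90 will be unaware of the stent. That sentence follows the mention of the day-90 return and the discussion of next steps, so it can equally describe care at day 90.
- A reader might turn the section 16 hold into a length of delay in stent removal. The end point of the hold is undefined, and the hold concerns results, not treatment.
- A reader might assume that everyone who reaches day 90 is told the allocation and has the stent out. Table 1 makes removal conditional, and scenario 2 allows the subject to stay blinded to allocation. The contrast is narrower: from day 90 someone who knows the stent status must advise the subject, and before then nobody must.

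**Conclusion.** The gap is real in the protocol text. Followed literally, sections 13 and 16 allow a blinded subject to leave with a stent that nobody is required to mention, although the protocol names that device's risks and plans advice on removal even for subjects who are well.

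The size is modest. The number affected cannot be derived, is bounded by 15, and is likely small. No endpoint, estimate or analysis is affected. The text does not show that any subject would in fact go uninformed, nor that section 16 forbids telling them. This is a cheap improvement on patient-safety grounds, not a fault in the trial's inference.

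The conclusion rests on two assumptions: that most endotherapy subjects are stented, as sections 3.1 and 10.1.2 imply, and that the unseen consent pages hold no equivalent exit instruction. If they do, the remaining task is to bring the protocol into line with them.

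**What to change.** Add to section 13: on full consent withdrawal, or a stop by the investigator or sponsor, before stent removal, the unblinded treating endoscopist checks the recorded stent status, tells the subject of any stent in place (and the treating physician, as permitted), and refers for removal or management per standard of care.

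Add to section 16: the hold on day-0 results does not apply to this disclosure. With that exception written in, the undefined end of the hold no longer matters for this purpose.

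The cost is two or three sentences. The stent data and the unblinded role already exist. The downside is that a few subjects who have already left blinded follow-up are unmasked; the blind of those who remain is untouched.
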